## 9 STATISTICAL CONSIDERATIONS

### 9.1 Sample size determination

This is a descriptive study. The planned sample size is 12 enrolled subjects. For the study to be a success, at least 9 of 12 subjects must be consented, enrolled and complete the study. If at least 9 of 12 subjects complete the study, the lower bound of the 95% exact binomial confidence interval for the completion rate will exceed of 34%.

### 9.2 Population for Analyses

A modified intent-to-treat data set will be used for both safety and efficacy endpoint analysis. All subjects who have received one dose of study medication will be included in all efficacy and safety data sets. Subjects who fail to begin study therapy will be replaced.

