### **4.2 End of Study**

A subject is considered to have completed the study if he or she has completed all phases of the study including the last visit or the last scheduled procedure shown in the Schedule of Events.

The study will end when the last subject completes the last visit or last contact, discontinues from the study, or is lost to follow-up, whichever occurs first. In addition, the sponsor may terminate the study at any time. If at any time, the sponsor terminates the study any subjects receiving clinical benefit from the study intervention may roll over to an expanded access protocol, if available, to ensure continued access to the study medication.

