## 5 STUDY POPULATION

Potential study participants must meet all inclusion criteria and no exclusion criteria to be deemed eligible for trial participation. To ensure subject safety, all subjects must be deemed eligible at the time of study registration and must continue to meet eligibility criteria up to ketamine dosing. This eligibility checklist is used to determine subject eligibility and will be filed with the enrolling investigator's signature in the subject research chart.

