## 5.4 Screen Failures

Screen failures are defined as participants who consent to participate in the clinical trial but do not meet subject eligibility criteria. These subjects will not be entered into the study or begin study intervention. However, minimal information is required to ensure transparent reporting of screen failure participants to meet the Consolidated Standards of Reporting Trials (CONSORT) publishing requirements. Minimal information includes, but may not be limited to, demography, screen failure details, eligibility criteria, and any serious adverse event (SAE) experienced during screening, but prior to being deemed ineligible. Adverse events and SAEs will not be collected after a subject is deemed ineligible. Any AEs/SAEs related to a screening procedure will be followed until resolution.

Individuals who do not meet the criteria for participation in this trial (screen failure) may be rescreened at the Investigator's discretion.

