### 5.5.1 Number of Subjects

The study will enroll 12 subjects.

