### 9.3 Primary Endpoint

To assess the feasibility of recruiting, consenting, enrolling, and completing the study intervention for 12 patients.

Primary endpoint: The recruitment, consent, enrollment, and study completion of 12 patients. Study completion defined as participating in at least 2/3 of the 3 KAP sessions.

All subjects who enroll on the study will be considered evaluable. The completions rate will be reported along with a 95% exact binomial confidence interval (Clopper-Pearson method).

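### Once a subject who never starts therapy is replaced, 13 enrolled subjects are evaluable and the 9-of-12 success rule no longer matches its denominator

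*Combined protocol and SAP*

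**What the plan says.** Four statements in the combined protocol and SAP bear on the primary success call.

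- Section 5.5.1: "The study will enroll 12 subjects". Section 9.1 gives the same planned size.
- Section 9.1, the only success criterion for the primary endpoint: "For the study to be a success, at least 9 of 12 subjects must be consented, enrolled and complete the study".
- Section 9.2, after two sentences defining a modified intent-to-treat set (one dose received) for safety and efficacy: "Subjects who fail to begin study therapy will be replaced". The feasibility endpoint is not mentioned.
- Section 9.3: "All subjects who enroll on the study will be considered evaluable". The completion rate is reported with a 95% Clopper-Pearson interval. Completion is defined there: "Study completion defined as participating in at least 2/3 of the 3 KAP sessions".

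Section 6.3.2 allows drug to be dispensed only to enrolled subjects. Enrolment therefore precedes dosing, and an enrolled subject who never starts can exist.

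**The concern.** A replacement is enrolled, so under section 9.3 that subject is evaluable, and so is the subject replaced. After one replacement the primary denominator is 13, while the success rule is still written for 12. Three readings are open: nine completers whatever the number enrolled (or 9 of the 12 who started), 9 of the first 12 enrolled, or the same 75% of all enrolled. The same data can pass one reading and fail another.

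The first reading matters most. Failing to start is one of the ways in which feasibility can fail, and under that reading a non-starter no longer counts against success. No error rate is at stake, because section 9.1 calls the study descriptive. But 9 of 12 is the only bar set for the primary endpoint, and section 3.1 says the study will inform a larger randomised trial.

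**Working it through.** **The plan's own figure.** Section 9.1 says that with at least 9 of 12 completing, the lower 95% exact limit exceeds 34%. The Clopper-Pearson lower limit is the 0.025 quantile of Beta(x, n-x+1).

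- 9/12: Beta(9, 4) gives 42.8% (interval 42.8-94.5%).
- 8/12: Beta(8, 5) gives 34.9% (interval 34.9-90.1%).

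The stated inequality is true for 9/12, but 34% is not the limit for that result; it fits 8/12. This is a separate matter, and the present point does not depend on it.

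**Worked example with one replacement.** Of the first 12 enrolled, 1 never starts, 8 complete and 3 start but do not complete. The replacement starts and completes.

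| Reading | Result | Success? |
|---|---|---|
| First 12 enrolled | 8/12 = 66.7% (34.9-90.1%) | No |
| Nine completers, or 9 of 12 starters | 9 completers | Yes |
| 75% of all enrolled | 9/13 = 69.2% (38.6-90.9%) | No; 10/13 = 76.9% would be needed |

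The rate that section 9.3 would report is 9/13 under every reading.

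**How often the readings would differ.** The documents give no start or completion rates, so these are assumptions. Let each enrolled subject start with probability s and, having started, complete with probability c, independently, with replacements behaving the same way.

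- First 12 enrolled, non-starters counted as non-completers: P(Bin(12, s × c) ≥ 9).
- Nine completers, with replacement until 12 have started: P(Bin(12, c) ≥ 9).

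With s = 0.90:

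| c | s × c | First 12 enrolled | Nine completers, 12 starters | Difference (points) |
|---|---|---|---|---|
| 0.70 | 0.63 | 29% | 49% | 20 |
| 0.80 | 0.72 | 55% | 79% | 24 |
| 0.90 | 0.81 | 82% | 97% | 15 |

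The start rate matters as much. At c = 0.80 the two probabilities are 43% and 79% for s = 0.85, and 68% and 79% for s = 0.95. At c = 0.90 and s = 0.95 they are 92% and 97%. At s = 1 both formulas reduce to P(Bin(12, c) ≥ 9), so there is no difference.

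**Chance that the question arises.** The probability that at least one of the first 12 never starts is 1 - s^12: 86%, 72% and 46% for s = 0.85, 0.90 and 0.95.

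**The case against.** The strongest reply is that section 9.3 already protects the analysis. With all enrolled subjects evaluable, a non-starter counts as a non-completer in the reported rate and interval. In section 9.2 the replacement sentence follows text on the safety and efficacy set, so its natural purpose is to keep 12 treated subjects. Both points stand. A reader might infer that replacement inflates the reported completion rate; the documents do not support that. What is left is the success call. Even when replacement serves only the treated sets, the replacement is enrolled, the denominator exceeds 12, and the rule is not restated.

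The ambiguity also runs both ways. Requiring 75% of all enrolled is stricter than judging the first 12: 48% against 55% at s = 0.90 and c = 0.80, with replacement until 12 start. And the differences above are largest with unlimited replacement; with at most one replacement, nine completers has a 69% chance in that same case. These points limit the size but do not remove the gap.

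Four stronger readings are tempting and should not be drawn:

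- **The escort rule in section 6.2.2 shows that non-starters are likely.** It withholds a dose at a session. It does not say the subject is never treated, and inclusion criterion 17 already requires an escort. Withdrawal and deterioration (section 6.7.1) are better grounds.
- **Two completion definitions undermine 9 of 12 even without replacement.** Section 4.2 does say "A subject is considered to have completed the study if he or she has completed all phases of the study including the last visit", but it deals with the end of the study. The synopsis and sections 2.1 and 9.3 define study completion for this endpoint by KAP sessions, and that definition reasonably governs section 9.1.
- **The screen-failure text shows that registered subjects can be removed from the denominator.** Section 5 says "all subjects must be deemed eligible at the time of study registration and must continue to meet eligibility criteria up to ketamine dosing", and section 5.4 says of screen failures "These subjects will not be entered into the study or begin study intervention". How a subject who loses eligibility between registration and dosing is classed is a missing detail, not evidence of removal.
- **The absence of a cap on replacements is itself the fault.** A cap would not settle the matter, since a single replacement is enough to raise the question.

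**Conclusion.** The point holds as a conflict between stated rules. Replacement under section 9.2 and evaluability under section 9.3 can take the primary denominator above 12, while the success rule in section 9.1 is fixed at 9 of 12. Read as nine completers or as 9 of 12 starters, the rule can turn 8/12 into a success while the reported rate is 69.2%, below 75%.

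The effect is conditional: it needs at least one replacement and touches only the success call. Its size rests on assumed rates, independence between subjects and, for the largest differences, replacement until 12 have started. At a 90% start rate it is 15 to 24 percentage points for completion given start between 70% and 90%; it is smaller at higher start rates and zero if everyone starts. Because this is the only success criterion and the remedy is wording, it should be fixed before results are known.

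**What to change.** - **Section 9.2:** state that replacement serves only the treated (safety and efficacy) sets and removes nobody from the primary endpoint.
- **Sections 9.1 and 9.3:** state that enrolled subjects who never start count as non-completers, that 9 of 12 is judged on the first 12 enrolled, and that the completion rate and Clopper-Pearson interval for all enrolled, including replaced subjects and their replacements, are reported beside it.
- **Section 5.5.1:** allow enrolment above 12 for replacements.
- **Minor alignment:** have section 9.1 refer to the completion definition in section 9.3 (at least 2 of the 3 KAP sessions).

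The cost is protocol wording. The downside is a success rule that is harder to meet than nine completers, by 15 to 24 percentage points in the 90% start-rate examples. The success call and the reported rate would also have different bases and could look inconsistent: 9 of the first 12 is a success, but if two replacements both fail to complete, the reported rate is 9/14 = 64.3%. Reporting both with their denominators makes this visible. A threshold for each number enrolled (10/13, 11/14) would also resolve the conflict, provided it is fixed in advance.

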### 9.3 Primary Endpoint

To assess the feasibility of recruiting, consenting, enrolling, and completing the study intervention for 12 patients.

Primary endpoint: The recruitment, consent, enrollment, and study completion of 12 patients. Study completion defined as participating in at least 2/3 of the 3 KAP sessions.

All subjects who enroll on the study will be considered evaluable. The completions rate will be reported along with a 95% exact binomial confidence interval (Clopper-Pearson method).

### 9.4 Secondary Endpoints

#### 9.4.1 The frequency of adverse events (AEs) and serious adverse events (SAEs) characterized by type, severity (as defined by the NIH CTCAE, version 5.0), seriousness, duration, and relationship to study treatment.

All subjects who receive any study treatment will be included in the final summaries and listings of safety data. The detailed information collected for each AE will include a description of the event, duration, severity, relatedness to study drugs, action taken, and clinical outcome. The severity of the AEs will be graded according to the CTCAE v5.0. The statistical analysis of the safety data will be descriptive and tabular.

#### 9.4.2 The proportion of screened patients that meet criteria on the Existential Distress Scale (EDS: Single domain $\geq 3$ or total score $\geq 6$ ).

All patients who have been consented to the study will be included in the final analysis.

The observed proportion will be reported along with a 95% exact confidence interval.

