#### 2.2.2 To determine the prevalence of existential distress in patients with non-operable GI cancers.

Secondary Endpoint: The proportion of screened patients that meet criteria on the Existential Distress Scale (EDS: Single domain  $\geq 3$  or total score  $\geq 6$ ).

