## 5.3 Registration

Subjects must complete all screening procedures and meet all of the eligibility requirements before registration. Study-related screening procedures can only begin once the subject has signed the consent form. Subjects must not begin protocol treatment prior to registration.

Treatment should start as soon as logistically possible after registration.

To register eligible subjects on study, complete a Clinical Trials Office Subject Registration Form and submit to [[contact]](mailto:[contact]).

For sites outside of Huntsman Cancer Institute, submit registration forms to [[contact]](mailto:[contact])

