## 5.5 Strategies for Recruitment

Potential patients will be identified by Investigators in the setting of their outpatient clinics. Social work team members on each oncology service will help identify potential patients during routine clinic encounters.

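### Objective 2.2.2 promises a prevalence of existential distress, but section 9.4.2 estimates a screening yield among patients who consented to the ketamine trial

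*Combined protocol and SAP*

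**What the plan says.** The objective in section 2.2.2 is "To determine the prevalence of existential distress in patients with non-operable GI cancers". The endpoint beneath it is narrower: "The proportion of screened patients that meet criteria on the Existential Distress Scale", positive meaning any single domain at 3 or more or a total of 6 or more. Section 9.4.2 then fixes who is counted, "All patients who have been consented to the study will be included in the final analysis", and how the result is presented: "The observed proportion will be reported along with a 95% exact confidence interval".

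Four other places determine who reaches that denominator.

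- Section 5.5: "Potential patients will be identified by Investigators in the setting of their outpatient clinics", and "Social work team members on each oncology service will help identify potential patients during routine clinic encounters".
- Section 5.3: "Study-related screening procedures can only begin once the subject has signed the consent form". The Schedule of Events lists the EDS as a screening assessment.
- Sections 4 and 5.1: the trial is for patients who have existential distress, and EDS positivity is inclusion criterion 3.
- Section 5.4: patients who fail screening "may be rescreened at the" investigator's discretion.

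**The concern.** The objective names one population and the estimator uses another. A patient is counted only after being identified as a potential participant and agreeing to enter a treatment trial for the condition being measured. If either step depends on distress, the observed proportion moves away from the prevalence in the named population, and an exact binomial interval does not show it. A reader of the results could take the proportion and its interval as a prevalence for non-operable GI cancer. Section 3.1 says the study will inform a larger randomised trial, so a mislabelled figure could also distort an estimate of the eligible pool.

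Two counting rules are also unsettled, and they affect the reported number even under a correct label: what happens to consented patients with no EDS, and which EDS counts for a patient screened more than once.

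**Working it through.** **Path into the denominator.** Identified in clinic (5.5), then consent (5.3), then EDS at screening (Schedule of Events), then counted (9.4.2). The documents describe no consecutive or random sampling, no EDS for patients who decline or are not approached, no adjustment, and no stated limitation. The screening log in section 11.1 covers screened subjects only.

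**The plan's own figure.** There is none to reproduce: no expected proportion, number to be screened or precision is stated for this endpoint. The 34% bound in section 9.1 concerns the completion rate and does not bear on this point.

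**Illustration of the bias.** Inputs:

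- True proportion π of 25% and 50%, the ends of the background range in sections 3 and 3.2.
- k, the chance that an EDS-positive patient is identified and consents, relative to an EDS-negative patient. This is an assumption; the documents give no value.
- 12 EDS-positive patients among N consented. This is the minimum for full enrolment of 12, because positive patients excluded on other criteria would also count.

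Expected proportion = kπ / (kπ + 1 − π). For π = 25% and k = 2: 0.50 / (0.50 + 0.75) = 40%, a bias of 15 points. Then N = 12 / 0.40 = 30, and the two-sided 95% Clopper-Pearson interval for 12/30 is 22.7% to 59.4%, half-width 18.4 points. The other rows follow in the same way.

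| π | k | Expected | Bias (points) | 12/N | 95% exact CI | Half-width |
|---|---|---|---|---|---|---|
| 25% | 0.5 | 14.3% | −10.7 | 12/84 | 7.6-23.6% | 8.0 |
| 25% | 1 | 25.0% | 0 | 12/48 | 13.6-39.6% | 13.0 |
| 25% | 2 | 40.0% | +15.0 | 12/30 | 22.7-59.4% | 18.4 |
| 25% | 3 | 50.0% | +25.0 | 12/24 | 29.1-70.9% | 20.9 |
| 25% | 4 | 57.1% | +32.1 | 12/21 | 34.0-78.2% | 22.1 |
| 50% | 0.5 | 33.3% | −16.7 | 12/36 | 18.6-51.0% | 16.2 |
| 50% | 1 | 50.0% | 0 | 12/24 | 29.1-70.9% | 20.9 |
| 50% | 2 | 66.7% | +16.7 | 12/18 | 41.0-86.7% | 22.8 |
| 50% | 3 | 75.0% | +25.0 | 12/16 | 47.6-92.7% | 22.6 |
| 50% | 4 | 80.0% | +30.0 | 12/15 | 51.9-95.7% | 21.9 |

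The bias exceeds the half-width at k = 3 and 4, but not at k = 2. Among the six rows with k of 2 to 4, the interval misses the true value in three: π = 25% with k = 3 or 4, and π = 50% with k = 4. With k = 0.5 the bias is downward and slightly larger than the half-width. More than 12 positives would narrow every interval and leave the bias unchanged.

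**Denominator.** Section 2.2.2 counts screened patients and section 9.4.2 counts all consented patients. The two differ for anyone who consents and leaves, or fails another criterion, before completing the EDS. As an assumed example, with 12 positives among 24 completed scales and 3 further consented patients without one, the literal rule gives 12/27 = 44% and the completed-EDS rule gives 12/24 = 50%.

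**Rescreening.** A negative EDS is a screen failure under criterion 3, and section 5.4 allows rescreening. If a later positive replaced a first negative, the proportion would rise. The plan neither adopts nor excludes this.

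**The case against.** The strongest reply is that the operative text is already accurate. The endpoint and the heading of 9.4.2 speak of screened patients, and the text promises an observed proportion, so only the objective overreaches. That is largely right, and it is why the remedy is mostly wording. But the objective is what the endpoint is meant to answer, and nothing in the plan tells the reader that it does not.

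A reader might infer that the estimate must be too high. Upward bias is plausible, because the trial is aimed at distressed patients and needs a positive EDS for entry. The documents do not establish it. Section 5.5 does not say that patients are picked out for perceived distress. The exclusions in section 5.2 for severe depression, suicidal ideation and other psychiatric conditions could keep highly distressed patients from being approached.

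A reader might also infer that the bias outweighs the sampling error in general. At k = 2 it does not with 12 positives. The 25-50% range is also a loose benchmark: it is an upper-end estimate for advanced cancer and is not tied to this EDS rule, which is permissive (one of 10 items at 3 or more, or 6 of a possible 40). If true positivity were 70-80% (assumption), the bias at k = 2 would be only 12.4 to 8.9 points (82.4% against 70%; 88.9% against 80%).

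Section 7.1.1 lets standard-of-care procedures done before consent count towards screening. Nothing says the EDS is routine in these clinics, and 9.4.2 still counts only those who consented.

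Finally, screened and consented patients nearly coincide, and no text says that a rescreen replaces the first score. Both are true. These are gaps to close rather than demonstrated errors in a result.

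**Conclusion.** The point holds as a mismatch between objective and estimator. Following section 9.4.2 yields the EDS-positive proportion among clinic-identified patients who consented to the KAP trial. That does not answer objective 2.2.2, whichever way selection runs, and the exact interval does not repair it. This conclusion needs no assumed number.

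The size does. Across k = 0.5 to 4 and a true value of 25-50%, the expected proportion ranges from 14% to 80%, with a bias from −17 to +32 points. These figures show how far selection could move the result; they do not predict it.

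The consequence is limited. This is a secondary endpoint of a descriptive pilot, and no sample size, success rule or stated decision depends on it. It should still be changed, because it alters what the trial may conclude and because the literal denominator includes patients whose EDS status is unknown.

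**What to change.** Reword sections 2.2.2 and 9.4.2, and the matching synopsis lines, to *the proportion screening positive on the EDS among patients who consent to the KAP study*. State that it will not be reported as a population prevalence.

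Set the denominator to unique consented patients with a completed EDS, using each patient's first EDS whatever happens at rescreening. Report the number of consented patients without an EDS separately. Keep the 95% exact interval.

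The cost is protocol wording and one counting rule, with no new visits, patients or procedures. The downside is a less ambitious secondary claim.

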### 9.5 Exploratory Objectives

Exploratory endpoints include 1) the mean change in score on EDS and QIDS-SR-16 from baseline to 2 weeks post completion of intervention; 2) the correlation between total score on the MEQ-30 and NADA and change in the EDS score at the 2 week primary outcome time point;

and 3) the mean change in score on FACIT-Sp from baseline to Day 30 post completion of intervention.

An additional exploratory objective is to develop an algorithm with Storyline Health technology to rapidly discover the most predictive and information rich components in the assessment of burnout and its treatment response. The associated endpoints are 7) the identification of a behavioral phenotype that better predicts a response to ketamine intervention; and 8) the Storyline questionnaire completion rate.

Analysis of the above exploratory endpoints will be descriptive. Continuous variables will be summarized by the minimum, maximum, mean, standard deviation, and 95% confidence interval. The Storyline completion rate and 95% exact binomial confidence interval will be reported. Spearman rank correlation coefficients will be used to summarize the correlation between the total score on the MEQ-30 and NADA and change in the EDS score at the 2-week primary outcome time point.

